8.4 Consolidation Therapy

a. Dose Modifications for ATRA Toxicity during Consolidation Therapy

- Follow dose modifications outlined in Section [8.3a](#).
- The ATRA syndrome (see Section [7.3b](#)) is not expected in patients in CR or PR; however, if the syndrome is suspected, discontinue ATRA, start dexamethasone at 10 mg IV or PO BID, and contact the Study Chair.
- Patients who experienced severe or recurrent ATRA-related toxicity during induction that necessitated permanent discontinuation should be discussed with the Study Chair before reinstating ATRA during consolidation. Such patients can remain on protocol treatment without continuation of ATRA.

b. Dose Modifications for Gemtuzumab Ozogamicin (G.O.) during Consolidation

- Hepatotoxicity

If CTCAE 3.0 Grade 2-3 AST, ALT, or bilirubin elevation occurred during induction therapy (thought to be drug-related, and not disease related), G.O. dose will be reduced to 6 mg/m² during Consolidation Cycle 5. If Grade 2-3 AST, ALT, or bilirubin elevation recurs following Day 1 of G.O. during Consolidation Cycle 5, the dose of G.O. during Consolidation Cycle 6 will be decreased to 3 mg/m².

For patients in whom Grade 2-3 AST, ALT, or bilirubin elevation did NOT occur during induction, but occurs following Day 1 of Consolidation Cycle 5, the dose of G.O. during Consolidation Cycle 6 will be decreased to 6 mg/m².

For patients that experience Grade 4 AST, ALT, or bilirubin elevation following G.O. during any course, further G.O. will NOT be administered. In these instances, a hepatic doppler ultrasound is required to evaluate for hepatic sinusoidal obstructive syndrome.

In any case where there is Grade 3 bilirubin elevation, a hepatic doppler ultrasound is recommended to evaluate for hepatic sinusoidal obstructive syndrome.

- Hematologic Toxicity

Following the initiation of Consolidation Cycle 5, delayed recovery of peripheral blood to B1 status (see Section [10.1](#)) beyond 8 weeks will require discontinuation of further G.O. therapy, and patients will proceed to Maintenance Therapy.

- Anaphylactic reaction

For patients experiencing anaphylactic reaction with this agent during induction, gemtuzumab ozogamicin will be permanently discontinued.

c. Dose Modification for Daunomycin during Consolidation

- Hepatotoxicity (for patients with evidence of hepatic dysfunction, reassess regularly during daunorubicin treatment).**

Bilirubin	% Dose to Give
> 3.0 mg/dL	75%

- Cardiotoxicity:** Adequate LV function will be required as described previously. Patients judged not to have adequate LV function should be discussed with the Study Chair.

d. Dose Modifications for Arsenic Trioxide during Consolidation

- See Section [8.3.b](#) above. For patients requiring dose reduction of arsenic trioxide during induction due to toxicity, the starting dose for consolidation should be reduced to the acceptable dose determined during induction. For patients in whom arsenic trioxide was permanently discontinued during induction therapy, arsenic trioxide will be omitted from Consolidation Cycles 1 and 2, and patients will proceed to Consolidation Cycle 3. For patients experiencing toxicity from arsenic trioxide during consolidation (in the absence of previous toxicity during induction), dose adjustment guidelines as stated in Section [8.3b](#) should be followed.

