Percentages estimated in adults > 60 years of age. < 1% (limited to significant and/or life threatening): Hepatic failure, jaundice, hepatosplenomegaly, veno-occlusive disease.

Hypersensitivity: Gemtuzumab ozogamicin administration can result in severe hypersensitivity reactions (including anaphylaxis), and other infusion-related reactions which may include severe pulmonary events. Infrequently, hypersensitivity reactions and pulmonary events have been fatal. In most cases, infusion-related symptoms occurred during the infusion or within 24 hours of administration of gemtuzumab ozogamicin and resolved. Gemtuzumab ozogamicin infusion should be interrupted for patients experiencing dyspnea or clinically significant hypotension. Patients should be monitored until signs and symptoms completely resolve. Discontinuation of gemtuzumab ozogamicin treatment should be strongly considered for patients who develop anaphylaxis, pulmonary edema, or acute respiratory distress syndrome. Physicians should consider leukoreduction with hydroxyurea or leukapheresis to reduce the peripheral white count below 30,000 prior to administration of gemtuzumab ozogamicin.

Overdosage/Toxicology: Symptoms are unknown. General supportive measures should be instituted. Gemtuzumab ozogamicin is not dialyzable.

Drug Interactions: No formal drug interaction studies have been conducted.

Pregnancy/Breast-Feeding Implications: May cause fetal harm when administered to a pregnant woman. Women of childbearing potential should avoid becoming pregnant while receiving treatment. If used in pregnancy, or if patient becomes pregnant during treatment, the patients should be apprised of potential hazard to the fetus. Excretion in breast milk unknown, breast feeding is not recommended.

c. PHARMACOLOGY

Kinetics: Half-life: Total calicheamicin: 45 hours (initial dose); 60 hours on repeat dosing. Unconjugated calicheamicin: 100 hours (no change noted in repeat dosing).

Formulation: Powder for injection: 5 mg.

Storage and Stability: Light sensitive; protect from light. Store vials under refrigeration 2° to 8°C or 36° to 46°F. Reconstituted vials may be stored under refrigeration for up to 8 hours.

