- d. Patients who cannot receive daunomycin because of cardiac or other toxicity, or are unable to initiate Consolidation Cycle 4 within 8 weeks of recovering peripheral blood counts to B1 status, must be discussed with the Study Chair; if in CR, these patients will proceed to Consolidation Cycle 5.

e. Consolidation Cycles 3 and 4 Treatment Plan

AGENT	DOSE	ROUTE	Time	NOTES
ATRA	45 mg/m ² /day (in 2 doses, 22.5 mg/m ² every 12 hours)	PO	every 12 hours, Days 1-7	With food. See Section 7.5e below.
Daunomycin*	50 mg/m ² /day	IV bolus or 1 hour infusion	Days 1-3	

* Idarubicin, 12mg/m²/day, on Days 1-3, may be used in place of daunomycin only if daunomycin is unavailable due to the national shortage. This must be documented on the **S0535** Consolidation Cycles 3 and 4 Treatment Summary Form.

- f. ATRA will be “rounded” up to the nearest 10 mg, divided into 2 daily doses, given orally every 12 hours with food.
- g. Prior ATRA syndrome: Patients who experienced the ATRA syndrome during induction may receive ATRA during Consolidation Cycles 3 and 4, since the ATRA syndrome is not expected to occur during remission.

7.6 Consolidation Cycles 5 and 6

- a. Patients who remain in B1 peripheral blood, and C1 extramedullary disease status (see Section [10.1](#)) may continue consolidation therapy. Consolidation Cycle 5 should be started no earlier than 2 weeks and no later than 8 weeks after recovery of peripheral blood counts to B1 status (see Section [10.1](#)).
- b. Consolidation Cycle 6 should be started no earlier than 2 weeks, and no later than 8 weeks after recovery to B1 peripheral blood status.
- c. Patients who cannot receive gemtuzumab ozogamicin because of previous toxicity or who are unable to initiate Consolidation Cycle 6 within 8 weeks after recovering peripheral blood counts to B1 status must be discussed with the Study Chair; if in CR, these patients will proceed to Maintenance Therapy.
- d. Consolidation Cycles 5 and 6 Treatment Plan

AGENT	DOSE	ROUTE	Time	NOTES
Gemtuzumab Ozogamicin ^Δ	9 mg/m ²	IV infusion over 2 hours	Day 1	

^Δ Recommended premedications prior to gemtuzumab: acetaminophen 1 gm orally, diphenhydramine 50 mg IV, and methylprednisolone 125 mg IV.

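### Section 8.4b makes anaphylaxis a mandatory stop for gemtuzumab only if it occurs in induction, so a first reaction in Cycle 5 leaves the Cycle 6 dose discretionary

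*Combined protocol and SAP*

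**What the plan says.** G.O. is given once in induction (Section 7.3) and once in each of Consolidation Cycles 5 and 6 (Section 7.6d). Section 8.4b covers its dose modification during consolidation. The anaphylaxis bullet there is: "For patients experiencing anaphylactic reaction with this agent during induction, gemtuzumab ozogamicin will be permanently discontinued".

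Three other provisions bear on a reaction in Cycle 5.

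- **Section 3.4b** (drug information, not tied to a phase): "Discontinuation of gemtuzumab ozogamicin treatment should be strongly considered for patients who develop anaphylaxis". It adds: "Infrequently, hypersensitivity reactions and pulmonary events have been fatal".
- **Section 7.6c**: "Patients who cannot receive gemtuzumab ozogamicin because of previous toxicity", or who cannot start Cycle 6 in time, "must be discussed with the Study Chair; if in CR, these patients will proceed to Maintenance Therapy".
- **Section 7.11d**: removal from protocol treatment for unacceptable toxicity, as defined in Section 8.0.

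Section 3.4 also refers sites to the package insert, which is not part of these documents.

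**The concern.** The section that governs consolidation dosing has an anaphylaxis rule that looks back only to induction. A patient can tolerate the induction dose, react for the first time in Cycle 5, and still have Cycle 6 scheduled. Read literally, the same reaction is an absolute bar if it happened in induction, but only a strong reason to consider stopping if it happened in Cycle 5. The protocol gives no reason for the difference, and it acknowledges that such reactions have occasionally been fatal.

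What is at stake is one avoidable re-exposure in a small number of patients. The statistical design is not involved.

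**Working it through.** The plan states no figure on this point, so the main check compares the text of the rules.

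**Which rules reach an event that first arises in Cycle 5?**

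| Provision | Covers a first event in Cycle 5? | Mandatory? |
|---|---|---|
| 8.4b, G.O., Grade 2-3 hepatic | Yes: "did NOT occur during induction, but occurs following Day 1 of Consolidation Cycle 5" | Yes, dose cut to 6 mg/m² in Cycle 6 |
| 8.4b, G.O., Grade 4 hepatic | Yes: "following G.O. during any course, further G.O. will NOT be administered" | Yes, stop |
| 8.4b, G.O., delayed count recovery | Yes, runs from the start of Cycle 5 | Yes, stop and go to Maintenance |
| 8.4d, arsenic trioxide | Arsenic is given in Cycles 1 and 2; the rule covers toxicity new in consolidation: "For patients experiencing toxicity from arsenic trioxide during consolidation (in the absence of previous toxicity during induction") | Yes, follow 8.3b |
| 8.4b, G.O., anaphylaxis | **No**, induction only | Not for Cycle 5 |

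Anaphylaxis is the only G.O. toxicity in 8.4b without a clause for a first event in consolidation.

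**Does another provision close the gap?**

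- 3.4b applies in any phase and names anaphylaxis, but it is advice. Its instruction to interrupt an infusion concerns the dose being given, not the next cycle.
- 7.6c says what happens to a patient who cannot receive G.O. It does not say that anaphylaxis makes a patient unable to receive it.
- 7.11d points to Section 8.0, and so back to 8.4b.
- Arsenic trioxide (8.3b) and 6-MP/methotrexate (8.5a) each have a catch-all for other toxicity of Grade 3 or worse. G.O. has none.

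None of these makes stopping mandatory.

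**Size.** The protocol gives no anaphylaxis rate for G.O., so *p* and *r* below are assumptions.

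- *n*, patients reaching Cycle 5. Low: 70 × 50% = 35 (3-year continuous CR under the null, Section 11.1). Middle: 70 × 70% = 49 (the alternative). High: 70 × 86% = 60.2, taken as 60 (pilot CR rate, Section 2.0). The high value is a ceiling, because CR is required for consolidation and not everyone in CR reaches Cycle 5. The low value is only a rough lower figure, because 3-year continuous CR is not the same as starting Cycle 5.
- *p*, first reaction at the Cycle 5 infusion: 0.5%, 1%, 2%.
- *r*, share of those patients still given Cycle 6: 5%, 10%, 25%.

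Expected first reactions = *n* × *p*: from 35 × 0.005 = 0.18 to 60 × 0.02 = 1.2.

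Expected re-exposures = *n* × *p* × *r*. Chance of at least one = 1 − (1 − *p* × *r*)^*n*.

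| *n*, *p* | *r* = 5% | *r* = 10% | *r* = 25% |
|---|---|---|---|
| 35, 0.5% | 0.009; 0.9% | 0.018; 1.7% | 0.044; 4.3% |
| 49, 1% | 0.025; 2.4% | 0.049; 4.8% | 0.12; 11.5% |
| 60, 2% | 0.06; 5.8% | 0.12; 11.3% | 0.30; 26.0% |

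Each cell gives expected re-exposures, then the chance of at least one.

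**The case against.** The strongest reply is that the protocol already makes unreviewed re-dosing unlikely. Section 3.4b advises strongly considering a stop. Section 7.6c provides a Study Chair discussion and a route to Maintenance that suits this patient. Under Section 16.1, serious Grade 4 or 5 events need 24-hour notification and a full report within 5 days, and serious Grade 3 events a report within 10 days. Section 8.8 sends reportable toxicities to the Study Chair. Cycle 6 cannot start until at least 2 weeks after count recovery (7.6b), so the Study Chair should know of a reported reaction before the dose is due. Section 3.4 also calls for premedication before each infusion. The package insert may say more, only one dose is affected, and the protocol is marked closed effective 06/01/2013.

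All of this lowers the likely harm and limits the priority of the point. None of it makes stopping mandatory, and it does not explain why the rule should depend on the phase in which the reaction occurred.

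The reply is also right that the sizes above rest on assumed rates. The 26% figure takes the highest value of all three inputs, and nothing in the documents supports re-dosing one patient in four against the advice in 3.4b. The table shows that expected re-exposures stay well below one; it does not estimate a risk.

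**Conclusion.** The point holds. Within these documents, no mandatory rule stops G.O. after a first anaphylactic reaction in Cycle 5. This is more than missing detail: a stated safety rule has the wrong scope, while its neighbours in the same section have the right one.

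It is a minor patient-safety correction. Under the assumed rates, about 0.2 to 1.2 first reactions are expected in Cycle 5. The chance of at least one re-exposure is about 1% to 11% if 5% to 10% of those patients are re-dosed, and about 4% to 26% if 25% are. The textual conclusion depends on none of these numbers. It is limited to the protocol as supplied, since the package insert was not available. The endpoints, error rates and sample size are not affected.

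**What to change.** In the anaphylaxis bullet of Section 8.4b, replace the limit to induction with the any-course scope used in the Grade 4 hepatic rule above it. Add that such patients, if in CR, proceed under Section 7.6c, which after a Cycle 5 reaction means Maintenance.

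The cost is one phrase and one cross-reference. At most 0.2 to 1.2 Cycle 6 doses would be forgone, if every such patient would otherwise have been re-dosed. At the assumed re-dosing shares the change removes only 0.01 to 0.30 doses, in patients for whom Section 3.4b already advises strongly considering a stop.

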8.5 Maintenance Therapy

- Dose Modifications for 6-MP and MTX during Maintenance Therapy
 - Because patients begin maintenance therapy in CR, the non-leukemia NCI CTCAE scale should be used during maintenance therapy.

Grade	ANC/mcl	and/or Hgb (g/dl)	and/or Platelets /mcl	6-MP & MTX
1	< LLN - 1,500	< LLN – 10	< LLN - 75,000	100%
2	< 1,500 - 1,000	8 - <10	< 75,000 - 50,000	50%
3	< 1,000 - 500	6.5 - < 8	< 50,000 - 25,000	0*
4	< 500	< 6.5	< 25,000	0*

* Discontinue 6-MP and methotrexate. Treatment may resumed at 50% doses when toxicity has resolved to \leq Grade 1. Both drugs may then be escalated individually to tolerance.

If more than one of the dose modifications apply, use the most stringent (i.e., the greatest dose reduction). The intent of this treatment is to give the highest tolerable daily dosages of 6-MP and oral methotrexate (up to 100%). If hematologic toxicity does not resolve, a bone marrow exam should be performed to evaluate for relapse.

- **Hyperbilirubinemia**

Give the following percentages of full dose:

Bilirubin (md/dL)	6-MP & MTX
< 3.0	100%
\geq 3.0 but < 5.0	75%
\geq 5.0	0*

* Hold treatment for up to four weeks. Contact the Study Chair if toxicity does not resolve.

- **Elevated ALT/AST**

Grade	ALT/AST	6-MP & MTX
1	> ULN – 2.5 X ULN	100%
2	> 2.5 – 5.0 X ULN	100%
3	> 5.0 – 20.0 X ULN	0*
4	> 20.0 X ULN	0*

* Discontinue 6-MP and methotrexate. When toxicity has resolved to \leq Grade 1, treatment with both drugs may resume with a 50% dose reduction. Both drugs then may be escalated individually to tolerance. If toxicity recurs, discontinue both drugs. Treatment may resume again after another 50% dose reduction (i.e., 25% of original dose) when toxicity resolves to \leq Grade 1. If toxicity reoccurs after a second dose reduction then discontinue drugs and contact the Study Chair. Persistent hepatic transaminase elevation may require liver biopsy for diagnosis.

The intent of this treatment is to give the highest tolerable daily dosages of 6-MP and weekly methotrexate that produce < Grade 3 toxicity.

- **Mucositis**

For \geq Grade 2 oral ulceration, hold oral methotrexate until mucositis clears, then reinstate at 75% of previous dose. Observe for hematologic toxicity if mucositis is noted.

- Other 6-MP or MTX-Related Toxicities: If Grade \geq 3, then hold treatment. Treatment may resume after a 50% dose reduction when toxicity resolves to \leq Grade 1. If toxicity reoccurs after a first dose reduction, treatment may resume again after another 50% dose reduction (i.e., 25% of original dose) when toxicity resolves to \leq Grade 1. If toxicity reoccurs after a second dose reduction then discontinue drug(s).

- Dose Modification for ATRA during Maintenance Therapy

- See Section [8.4.a](#) above

8.6 Dose Modifications for Obese Patients

There is no clearly documented adverse impact of treatment of obese patients when dosing is performed according to actual body weight. Therefore, all dosing is to be determined by the patient's actual weight. Failure to use actual body weight in the calculation of drug dosages will be considered a major protocol deviation. Physicians who are uncomfortable with administering chemotherapy dose based on actual body weight should not enroll obese patients on this protocol.

8.7 Dose Modification Contacts

For treatment or dose modification questions, please contact the Study Chair, [name] at [contact] or if [name] is not available, [name] at [name].

8.8 Adverse Event Reporting

Toxicities (including suspected reactions) that meet the expedited reporting criteria as outlined in [Section 16.0](#) of the protocol must be reported to the Operations Office, Study Chair and NCI via ADEERS, and to the IRB per local IRB requirements.

9.0 STUDY CALENDARS

REQUIRED STUDIES	PRE-STUDY	INDUCTION	CONSOLIDATION #1 through 2		CONSOLIDATION #3 through 4		CONSOLIDATION #5 through 6		MAINTENANCE		Follow Up
			Prior	During	Prior	During	Prior	During	Prior	During	
PHYSICAL											
History & Physical Exam	X	2X/week	X	X&	X	X α	X	X&	X	X&	X√
Height, Weight and BSA	X		X	X†	X	X†	X	X†	X	X&	X√
Performance Status (Zubrod)			X	X&	X	X α	X	X&	X	X&	X√
Toxicity Notation		2X/week	X		X		X		X	X&	X√
LABORATORY STUDIES											
CBC, Diff, Plts	X	2X/week	X	weekly	X	weekly	X	weekly	X	X&	X√
Pregnancy test	X										
Electrolytes (incl. Ca ⁺ and Mg ⁺⁺), creatinine *	X	2X/week	X	weekly	X	weekly	X	weekly	X	X&	
Bilirubin, AST, ALT, Alkaline phosphatase *	X	2X/week	X	weekly	X	weekly	X	weekly	X	X&	
Cholesterol, triglycerides *	X				X		X		X	X&	
PTT, PT, fibrinogen, FDP, D-dimer Δ *	X	2X/week									
BM Aspirate/Biopsy ⊖	X	X ψ	X		X				X	XΠ	X
Cytogenetics Σ	X	X ú									X¿
RT-PCR for PML-RARα Σ	X	X			X†				X		X¿
Lumbar Puncture (see Section 7.2b)			X								
X-RAYS AND SCANS											
Chest X-Ray %	X										
MUGA/ECHO					X#						
EKG \$	X	2X/week			X						
TREATMENT (See Section 7.0)											
Allopurinol/rasburicase		X									
ATRA		X f				X				X	
Daunomycin						X					
Arsenic trioxide		X		X							
6-mercaptopurine										X	
Methotrexate										X	
Gemtuzumab ozogamicin		X						X			

NOTE: Forms are found in Section 18.0. Forms submission guidelines are found in Section 14.0.

Click here to view [footnotes](#).

Footnotes:

- * Results of these tests do not determine eligibility but should be done prior to registration in accordance with good medical practice.
- & Monthly.
- √ After the patient is off treatment, the remaining of Months 3, 6, 9, 12, 18, 24 and 36 from the time of initial registration.
- Δ These tests should be done at pretreatment, twice weekly during induction until normal, and as clinically indicated thereafter.
- ⊖ Pretreatment, during induction (on Day 42, then q 2 wks until CR is met), prior to Consolidation #1, prior to Consolidation #3, prior to Maintenance, then every 3 months during maintenance. Once maintenance is complete, every 3 months for the 1st year, then every 6 months for the 2nd year, then at the end of the 3rd year from registration. Following completion of maintenance, only aspirate is required. Note that the marrow documenting CR may serve as the prior to Consolidation #1 marrow, providing it was performed within 8 weeks prior to Consolidation registration (see Section [5.2](#)).
- Σ See Section [15.0](#).
- % Chest X-Ray should be done pretreatment and as clinically indicated.
- \$ Obtain within 72 hours prior to the day of treatment. To be performed twice per week for the first 2 weeks of induction, prior to consolidation Cycle 3, and thereafter as clinically indicated.
- ψ On Day 42, then every 2 weeks until criteria for CR are met.
- π Every 3 months during maintenance.
- α Every 2 weeks.
- # See Section [7.5c](#).
- † To be performed prior to each cycle of consolidation.
- f ATRA administration is permitted for up to 5 days prior to registration.
- ¶ RT-PCR required prior to Consolidation #3, but not #4.
- ¿ Follow-up cytogenetics and RT-PCR required at relapse only.
- ü Only submitted centrally for patients affiliated with CALGB or ECOG (see Section [7.8a](#)).

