7.2 General Considerations

- a. Immediate measures to diagnose and begin treatment of infections should be instituted prior to induction therapy.
- b. A lumbar puncture is recommended following completion of induction, but not required. Prophylactic intrathecal chemotherapy may be given at the treating physician's discretion.
- c. All patients should be carefully followed serially with coagulation studies (PTT, PT, fibrinogen, FDP, and D-dimer). These tests should be done pretreatment, twice weekly during induction until normal and as clinically indicated thereafter. Optimal management of coagulopathy is controversial. Heparin usage is discouraged since all patients will be receiving ATRA; however, patients with either biochemical or clinical evidence of coagulopathy may be treated at the investigator's discretion.

- d. Additional electrolyte studies for calcium, magnesium, cholesterol and triglycerides should be obtained.
- e. Hydroxyurea therapy is permitted up to 24 hours before initiation of gemtuzumab ozogamicin (G.O.).
- f. All patients will be started on allopurinol 300 mg/day orally. For patients allergic to allopurinol, rasburicase may be substituted. Reversible abnormalities of metabolic function should be treated aggressively and corrected prior to institution of therapy.
- g. Investigators may contact the SWOG Study Chairs or Leukemia Committee Chair for assistance with the management of patients with high WBC count prior to confirmation of molecular diagnosis.

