7.3 Induction Chemotherapy

AGENT	DOSE	ROUTE	Time	NOTES
ATRA ^ζ	45 mg/m ² /day (in 2 doses, 22.5 mg/m ² every 12 hours)	PO	every 12 hrs, Day 1 to CR *	With food. See Section 7.3a below.
Gemtuzumab Ozogamicin ^Δ	9 mg/m ²	IV infusion over 2 hours	Day 1 only ^π	
Arsenic Trioxide	0.15 mg/kg/d	IV infusion over 2 hours	5 days/wk beginning on Day 10 and continuing until CR ^ψ	

* For maximum of 90 days, unless prohibited by either unacceptable toxicity or progressive disease.

^π G.O. may be delayed until Day 6 pending confirmation of APL diagnosis by FISH/cytogenetics, or RT-PCR. Hydroxyurea may be utilized during this time, up to 24 hours prior to initiation of gemtuzumab ozogamicin.

^ψ For a maximum of 60 days, unless prohibited by either unacceptable toxicity or progressive disease.

^Δ Recommended premedications prior to gemtuzumab: acetaminophen 1 gm orally, diphenhydramine 50 mg IV, and methylprednisolone 125 mg IV.

^ζ Day 1 of treatment will be the first day the patient is treated with ATRA, regardless of patient's registration status.

a. ATRA will be "rounded" up to the nearest 10 mg, divided into 2 daily doses, given orally every 12 hours with food.

b. **ATRA syndrome:** A spectrum of clinical manifestations of a cardiorespiratory distress syndrome has been described, including respiratory distress, hypoxemia, fever, erythematous rash, pulmonary infiltrates, pleural or pericardial effusions, congestive heart failure with impaired myocardial contractility and episodic hypotension. Patients with this syndrome may develop rapidly progressive cardiopulmonary failure.

If this syndrome is suspected, ATRA should be held and dexamethasone 10 mg IV or PO BID will be given for 3 days. ATRA will be resumed once the signs/symptoms of the syndrome have resolved. Patients with persistent signs/symptoms of the ATRA syndrome after 3 days of dexamethasone or who have recurrence of the ATRA syndrome after restarting ATRA should be discussed with the Study Chair.

- c. **Prolonged QT_c:** Prolongation of the QT_c has been reported with the use of arsenic trioxide in association with electrolyte abnormalities. Therefore, any identified electrolyte abnormalities of potassium, calcium, or magnesium should be promptly corrected to within normal limits prior to and during treatment with arsenic trioxide. EKG must be obtained twice weekly during induction therapy and as clinically indicated.

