7.8 Assessment of Response

a. Induction

A bone marrow aspirate and biopsy will be obtained at the time of neutrophil recovery ($\geq 1,000/\text{mcl}$) or on Day 42 after beginning protocol ATRA (i.e. not counting any days of ATRA given prior to the patients registration to this study), whichever comes first. Specimens of marrow aspirate (or peripheral blood if dry tap) must be submitted for cytogenetics (for patients affiliated with CALGB or ECOG) and PCR (for all patients) as described in Section [15.0](#). Subsequently, the bone marrow aspirate and biopsy will be repeated every 2 weeks until criteria for CR are met. These subsequent samples will NOT be submitted centrally for cytogenetic or RT-PCR testing, but the tests will still be performed locally. Testing for clinical/hematological CR should be performed locally for all of these subsequent specimens. Patients will continue ATRA and arsenic trioxide until CR is achieved, up to a maximum of 90 days. Patients with a CR will proceed to consolidation therapy as outlined above in Section [7.4](#).

b. Consolidation

A bone marrow aspirate and biopsy will be obtained within 8 weeks (preferably within 4 weeks) preceding Consolidation Cycle 1. This should be performed at the time when peripheral blood counts have recovered to baseline or as clinically indicated. A bone marrow aspirate and biopsy are also required prior to Consolidation Cycle 3. The pre-Consolidation Cycle 3 specimens of marrow aspirate (or peripheral blood if dry tap) must be submitted for PCR as described in Section [15.0](#).

c. Maintenance

A bone marrow aspirate and biopsy will be obtained within 8 weeks (preferably within 4 weeks) prior to beginning maintenance therapy. Specimens of marrow aspirate (or peripheral blood if dry tap) must be submitted for PCR testing as described in Section [15.0](#).

- d. A bone marrow aspirate and biopsy will be obtained every 3 months during Maintenance therapy. Specimens from these samples should NOT be submitted for RT-PCR testing or cytogenetics. Testing for clinical/hematological CR for these samples should be performed locally.

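### Footnote $ of the study calendar limits scheduled twice-weekly EKGs to the first 2 weeks of induction, while Sections 7.3c and 8.3b require them throughout induction

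*Combined protocol and SAP*

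**What the plan says.** In the Section 9.0 calendar, the Induction cell of the EKG row reads 2X/week. The row label carries footnote $, whose second sentence is: "To be performed twice per week for the first 2 weeks of induction, prior to consolidation Cycle 3, and thereafter as clinically indicated". Its first sentence, on an EKG within 72 hours before treatment, is not in question.

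Section 7.3c, on prolonged QTc during induction, says: "EKG must be obtained twice weekly during induction therapy and as clinically indicated". Section 8.3b repeats that sentence as the first item of its QTc guidelines, ahead of the rules that hold arsenic at 500-600 msec and above 600 msec.

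The Section 7.3 table gives arsenic "5 days/wk beginning on Day 10 and continuing until CR", and a footnote sets its limit: "For a maximum of 60 days, unless prohibited by either unacceptable toxicity or progressive disease". Another footnote fixes the day count: "Day 1 of treatment will be the first day the patient is treated with ATRA". Section 7.8a takes the first response marrow at neutrophil recovery or "on Day 42 after beginning protocol ATRA", whichever comes first.

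**The concern.** A footnote on a row label qualifies the cells of that row, so cell and footnote form one instruction: twice weekly, but only for two weeks. The section text has no such limit.

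The coagulation row shows the same structure working properly. Its 2X/week cell is narrowed by its footnote to "twice weekly during induction until normal, and as clinically indicated thereafter", and Section 7.2c sets the same limit: "twice weekly during induction until normal and as clinically indicated thereafter". Footnote $ has no counterpart in the section text.

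The limit also falls at an awkward time. Section 7.3c ties the EKG requirement to QTc prolongation on arsenic, and Section 3.2b lists that event as expected (less likely, up to 20%). The hold rules in 8.3b act on a measured QTc. Two weeks from the start of induction are mostly days before arsenic begins. A site that booked EKGs from the footnote would therefore schedule few of them on arsenic, and would depart from a mandatory sentence while appearing to follow the calendar.

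**Working it through.** The plan states no figure on this point, so there is none to reproduce. The check is the overlap between the footnote's window and the arsenic period.

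**Inputs**
- Window: the first 2 weeks of induction (footnote $).
- Arsenic start: Day 10, with Day 1 the first ATRA day (Section 7.3).
- ATRA allowed before registration: up to 5 days (Section 5.1e).
- Arsenic stop: CR, up to 60 days (Section 7.3). No time to CR is given, so stopping days are assumed: Day 42, from the marrow schedule; Day 69, which is 60 calendar days from Day 10; and Day 28, to illustrate an earlier CR.

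**Window, counted two ways**
1. From first ATRA: Days 1-14. Overlap with arsenic is Days 10-14: 14 − 10 + 1 = 5 calendar days.
2. From registration after 5 days of ATRA: the 2 weeks are Days 6-19. Overlap is Days 10-19: 19 − 10 + 1 = 10 calendar days.

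**Share of arsenic calendar days inside the window** = overlap / (stop day − 10 + 1)

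| Assumed stop | Arsenic days | Window to Day 14 | Window to Day 19 |
|---|---|---|---|
| Day 42 | 33 | 5/33 = 15% | 10/33 = 30% |
| Day 69 | 60 | 5/60 = 8% | 10/60 = 17% |
| Day 28 | 19 | 5/19 = 26% | 10/19 = 53% |

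Section 7.8a counts Day 42 from protocol ATRA. After 5 days of prior ATRA, that marrow falls on Day 47 from first ATRA, and the share is 10/(47 − 10 + 1) = 10/38 = 26%, inside the 15-30% range.

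**By doses.** With Monday-Friday dosing, Day 10 on any weekday and the window to Day 14, 3-5 doses fall inside it. To Day 42 that is 3-5 of 23-25 doses (13-20%); to Day 69, 3-5 of 42-44 (7-11%). If the 60-day maximum means dosing days, it is 3/60 to 5/60 (5-8%).

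**Scheduled EKGs on arsenic** = 2 × days / 7
- Sections 7.3c and 8.3b: 2 × 33/7 = 9.4 to Day 42; 2 × 60/7 = 17.1 to Day 69.
- Footnote $: 2 × 5/7 = 1.4 with the window to Day 14; 2 × 10/7 = 2.9 with the window to Day 19.

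**The case against.** The strongest reply is that a compliant path exists and is easy to find. The grid cell shows 2X/week with no limit inside it. The mandatory sentence appears twice, once at the head of the list that contains the hold rules, so anyone applying those rules meets it. A site following 7.3c and 8.3b also meets the footnote's minimum. Under-monitoring needs a site to let the footnote override all of this. That stands, and it limits who is affected.

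Other protections also remain. Sections 7.3c and 8.3b allow clinically indicated EKGs during induction. Section 8.3b requires rechecks once QTc reaches 500 msec. Electrolytes, including calcium and magnesium, stay at twice weekly in induction, and 7.3c requires abnormalities to be corrected before and during arsenic.

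A reader might infer that the protocol forbids or ends EKGs after Day 14, or that patients went unmonitored on arsenic. The documents support neither. The closing phrase of footnote $ can be read as applying after the two weeks or only after Cycle 3, but the section text permits indicated EKGs in either case. The documents also say nothing about what sites did.

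The October 2015 memorandum ruled for section text over a different Section 9.0 footnote. It concerned follow-up, so it is a precedent for the remedy and no evidence about EKGs. Not all memoranda and revision notices were available, so a separate correction of footnote $ cannot be excluded.

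None of this reconciles the wording. The current footnote still states a shorter schedule than two mandatory sentences.

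**Conclusion.** The inconsistency is real and should be corrected. Footnote $ sets a shorter EKG schedule than Sections 7.3c and 8.3b and narrows the calendar's own cell. Its window covers a minority of the arsenic period at the two main assumed stopping days: 15-30% at Day 42 and 8-17% at Day 69, the range reflecting where the two weeks start. The minority statement depends on those stopping days; with CR on Day 28 and the registration count, the share is just over half.

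The gap concerns scheduled monitoring only, at sites that put the footnote above the section text. A reader might also infer that the trial's conclusions are weakened. They are not weakened by this point: the joint decision rule, the 70-patient target and the stated error rates in Section 11.1 do not use the EKG schedule. Accrual closed on 06/01/2013, so the correction now serves deviation review and any reuse of the schedule. No claim is made about Consolidation Cycles 1 and 2, or about which arsenic maximum applies.

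**What to change.** Let Sections 7.3c and 8.3b govern. Keep the first sentence of footnote $ and reword the second along these lines: *EKGs twice per week throughout induction therapy, again before Consolidation Cycle 3, and at any time when clinically indicated.* This removes the two-week limit and the uncertainty over where the clinically indicated EKGs apply.

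The cost is one footnote edit, or a short clarifying memorandum of the kind issued in October 2015. It adds no procedure beyond what 7.3c and 8.3b already require. For deviation review, the memorandum could also say how sites that followed the footnote are to be treated.
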